#### 9.1.3 Events of Clinical Interest

Selected non-serious AEs and SAEs are also known as Events of Clinical Interest (ECI). This also includes immune-mediated AEs (see Appendix 7 for more details). Events of clinical interest for this trial include:

1. An overdose of pembrolizumab. For purposes of this trial, an overdose of pembrolizumab will be defined as any dose of 1,000 mg or greater ( $\geq 5$  times the indicated dose). No specific information is available on the treatment of overdose of pembrolizumab. Appropriate supportive treatment should be provided if clinically indicated. In the event of overdose, the subject should be observed closely for signs of toxicity. Appropriate supportive treatment should be provided if clinically indicated.
2. An elevated AST or ALT lab value that is greater than or equal to 3X the upper limit of normal and an elevated total bilirubin lab value that is greater than or equal to 2X the upper limit of normal and, at the same time, an alkaline phosphatase lab value that is less than 2X the upper limit of normal, as determined by way of protocol-specified laboratory testing or unscheduled laboratory testing.\*

\* **Note:** These criteria are based upon available regulatory guidance documents. The purpose of the criteria is to specify a threshold of abnormal hepatic tests that may require an additional evaluation for an underlying etiology.

#### **9.1.4 Reporting period**

Details of all treatment-related AEs will be documented and reported from the date of patient registration until 6 months after the administration of the last treatment. SAEs that are judged to be at least possibly related to IMP must still be reported in an expedited manner irrespective of how long after IMP administration the reaction occurred.

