				
 
Updated objectives and outcome measures, clarifying and summarising primary objectives and secondary and exploratory outcome measures
 
Updated Trial Design
 
Amended Inclusion and Exclusion criteria
 
Amended Patient Registration to receive a copy of the ICF
 
Treatment assessments updated to reflect changes in addition of and time when samples collected.
 
Updated Dose Modification and Toxicity Management section
 
Changed prohibited concomitant medications so that systemic steroids can be taken by patients have started trial treatment but steroids can only be taken for a maximum of 2 weeks
 
Added patients who meet RECIST criteria for progressive disease (PD) may be continued on trial treatment if the treatment is tolerable and believed to be of clinical benefit to Patient Withdrawal section.
 
During reporting period, only details of all treatment-related AEs will be documented.
 
Amended Dose Modification and toxicity management section
 
Amended pembrolizumab Infusion Reaction Dose modification and Treatment Guidelines table
 
Amended Statistical Considerations section
 

6	14 th August 2017	5.0	Substantial amendment	
 
Updated contact details
 
Specified instructions for collection and freezing of stool sample.
 
Correction of formatting errors
 

7	10-Jul-2018	6.0	Substantial amendment	
 
Trial contact details updated.
 
Table 4 updated.
 
Section 15: Regulatory framework updated.
 
Section 16: Updated to include General Data Protection Regulations.
 
Minor spelling and formatting changes throughout.
 

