### 7.10 Patient Follow up

After a patient is discontinued from trial therapy, a mandatory safety follow-up visit should be performed 28 days after the last infusion of trial medication. Procedures and assessments

performed at the safety follow-up visit should follow the respective guidelines described in the Schedule of Events. The patient will be monitored for all AEs monthly for up to 6 months and then 12 weekly during long term follow up.

For patients who start another cancer therapy before 28 days after discontinuation of trial therapy, the safety follow-up visit should occur prior to the patient receiving another cancer therapy. Follow up calls will be made every 12 weeks to record treatment after progression and death date if applicable.

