### 9.1 Reporting Requirements

#### 9.1.1 Adverse Events

All medical occurrences which meet the definition of an AE (see Appendix 7 for definition) should be reported. Please note this includes abnormal laboratory findings that are deemed clinically significant by the Investigator (abnormal laboratory findings that are not clinically significant are not AEs) or any pre-existing AEs that worsen by at least 1 CTCAE grade from baseline. If an AE changes grade, this should be reported as an individual AE.

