## Appendix 7: Adverse Event definition

### Adverse Event

Any untoward medical occurrence in a patient or clinical trial subject administered a medicinal product and which does not necessarily have a causal relationship with this treatment.

Comment:

An AE can therefore be any unfavourable and unintended sign (including abnormal laboratory findings), symptom or disease temporally associated with the use of an investigational medicinal product, whether or not related to the investigational medicinal product.

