## 8. TOXICITY AND SAFETY ANALYSIS

Adverse events will be recorded according to CTCAE v.4.0.

In addition to the analysis of the toxicity primary outcome, the statistician will report:

- The number (and %) of patients experiencing at least one any grade adverse event and adverse reaction (i.e. considered at least possibly related to pembrolizumab);
- The number (and %) of patients experiencing at least one grade 3-4 adverse event and adverse reaction (i.e. considered at least possibly related to pembrolizumab);
- The incidence of each adverse event and adverse reaction (all grades and grade 3-4) as a per-patient rate;
- The number of deaths considered to be associated with pembrolizumab;
- The number (and %) of patients experiencing at least one serious adverse event (SAE).

Additionally, we may present summaries of adverse events for those that are and are not immune-related.

The analysis population will be used.

Note: Adverse Events experienced within a Serious Adverse Event will be included in the AE and AR reporting.

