#### Toxicity

---

---

The toxicity co-primary outcome measure for the trial is defined as the occurrence of a treatment-related dose delay or treatment discontinuation due to an adverse event.

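### Protocol 9.1.1 and 7.10 require all adverse events but 9.1.4 only treatment-related ones, so the SAP's adverse event tables may be incomplete; the toxicity co-primary also needs its reading and data source stated

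*Protocol*

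**What the plan says.** On scope, protocol 9.1.1 states: "All medical occurrences which meet the definition of an AE (see Appendix 7 for definition) should be reported". Appendix 7 defines an adverse event as an occurrence "which does not necessarily have a causal relationship with this treatment", so unrelated events are included. Section 7.10 agrees: "The patient will be monitored for all AEs monthly for up to 6 months", and then continues at 12-week intervals in long-term follow-up.

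Section 9.1.4, the section that sets the reporting period, is narrower: "Details of all treatment-related AEs will be documented and reported from the date of patient registration", up to 6 months after the last treatment. The amendment table for version 4.0 describes the same restriction, so it looks intended.

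SAP section 8 reports adverse events and adverse reactions side by side, an adverse reaction being an event at least possibly related to pembrolizumab. The list includes: "The incidence of each adverse event and adverse reaction (all grades and grade 3-4) as a per-patient rate".

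The toxicity co-primary, worded alike in protocol 2.2.1.1 and 13.1.1 and in SAP 9.1.1, is "the occurrence of a treatment-related dose delay or treatment discontinuation due to an adverse event". The end of SAP 9.2.2 adds that a patient who reports no event meeting the criteria is counted as free of toxicity.

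**The concern.** A site cannot satisfy both 9.1.1 and 9.1.4 for an unrelated, non-serious event: one says report it, the other leaves it out. The SAP's adverse event figures have their meaning only if such events are recorded. In an open-label, single-arm trial of performance status 2 patients, attribution to drug or disease is a judgement with no control arm to check it. The all-cause figures are therefore the ones a reader would use to look past that judgement. If they are silently restricted, or restricted at some sites only, the reader cannot tell.

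The co-primary raises a related question. If discontinuation for any adverse event counts, the outcome needs information on unrelated events that 9.1.4 does not ask for on the AE form.

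**Working it through.** **Step 1: what each rule captures.** The inputs are protocol 7.10, 7.11, 9.1.1, 9.1.2, 9.1.4, 9.2.1.2 and 9.2.1.3, and SAP 8.

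| Event | If 9.1.1 and 7.10 govern | If 9.1.4 governs |
|---|---|---|
| Related, any grade | Recorded | Recorded |
| Unrelated, serious | Recorded | Recorded: 9.1.2 and 9.2.1.2 set no causality limit, and SAP 8 includes events within an SAE in its AE reporting |
| Unrelated, event of clinical interest | Recorded | Reported under 9.2.1.3 regardless of attribution |
| Unrelated, neither of these | Recorded | Not assured |

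Only the last row is at risk. The period differs too: 7.10 continues beyond 6 months, 9.1.4 stops there, and 9.1.4 gives no period for unrelated non-serious events.

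**Step 2: the two readings of the co-primary.**

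- If 'treatment-related' governs both delay and discontinuation, related-only collection is enough.
- If it governs delay only, stopping for an unrelated event counts as toxicity. The AE form need not hold that event under 9.1.4. Section 7.11 nevertheless requires the reasons for withdrawal in the CRF, and many such events would also be SAEs. The patient is miscounted only if the analysis uses AE forms alone, which SAP 9.2.2 neither requires nor rules out.

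**Step 3: where a miscount would matter.** The toxicity rule is Pr(rate < 0.30 | data) > 0.90, with prior logit(rate) ~ N(−2.2, variance 4) (protocol Table 9). The association parameter is ignored here. The posterior is proportional to prior × p^x (1 − p)^(60 − x).

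- Check against the plan: the prior mean is 0.203, and SAP Table 4 gives 0.20.
- Posterior probability at x = 13, 14 and 15: 0.944, 0.901 and 0.840. The limit is about 14 of 60.
- P(T ≤ 14 | 0.30) = 0.162 and P(T ≤ 15 | 0.30) = 0.244. SAP Table 6 shows approval of 0.175 to 0.182 in scenario 2 and up to 0.195 in scenario 10, both at 30% toxicity. The limit of 14 is therefore close but approximate.

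The recorded count cannot exceed the full count. The chance that one trial passes on the recorded count and fails on the full count is therefore P(T ≤ 14 | p − u) − P(T ≤ 14 | p), where u is the share of patients whose only qualifying event is missed. The documents give no value for u, so 2, 5 and 10 percentage points are assumed:

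| True rate p | Missed u | Pass, recorded | Pass, full | Difference |
|---|---|---|---|---|
| 30% | 2 points | 0.258 | 0.162 | 0.096 |
| 30% | 5 points | 0.451 | 0.162 | 0.289 |
| 30% | 10 points | 0.793 | 0.162 | 0.631 |
| 25% | 5 points | 0.793 | 0.451 | 0.342 |

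At lower true rates the effect nearly vanishes. P(T ≤ 14) is 0.971 at 15% and 0.999 at 10%, so the decision could change in at most 1 − 0.971 = 0.029 and 1 − 0.999 = 0.001 of trials.

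**The case against.** The best defence is that the protocol, taken as a whole, asks for all adverse events. Section 9 has investigators assess causality for all of them, 9.2.1.1 requires an AE form at each visit, the schedule has AE review at every cycle, and 9.1.4 is headed as a period rather than a scope. A site reading it this way would supply everything SAP 8 needs. That is right, and it means the tables are at risk, not lost. It does not remove the conflict: 9.1.4 is the only section that fixes the period, it names related events only, and the amendment table shows this was deliberate.

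Two stronger readings are tempting, and the documents support neither. A reader might infer that under 9.1.4 the adverse event and adverse reaction tables become identical. They would not, because unrelated SAEs and events of clinical interest are still collected.

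A reader might also infer that the discontinuation part of the co-primary cannot be produced. It can: 7.11 puts withdrawal reasons in the CRF, and if 'treatment-related' covers discontinuation, unrelated events are not needed at all. What stands is that the SAP neither settles the reading nor names the source.

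The figures in step 3 are also open to challenge. The missed shares are assumed, and they suppose that no SAE form, event of clinical interest report or withdrawal record recovers the event. They show where the rule is sensitive; they are not an estimate for this trial.

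**Conclusion.** The conflict over which adverse events are recorded is real and lies in the current text. If 9.1.4 is followed, SAP 8 would present as all-cause a set of events that lacks those that are unrelated, non-serious and not of clinical interest. If practice varies by site, the tables would mix two definitions. How many events this affects cannot be worked out from the documents.

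The co-primary issue is narrower: an ambiguous qualifier and an unnamed data source. It matters only if discontinuation for any adverse event counts, the outcome is taken from AE forms alone, and the count lies near the approximate limit of 14 in 60. There, one patient is enough: 15 true and 14 recorded passes. Because toxicity is a single parameter across all six cohorts, the change would reach the toxicity criterion in every cohort. Away from the limit it changes nothing.

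**What to change.** 1. Give 9.1.1, 7.10 and 9.1.4 one scope and one period. One way is to have 9.1.4 cover all adverse events, to match the other two, and to align its end date with the follow-up in 7.10. The cost is a wording change and some extra AE entry at visits already held.
2. If related-only collection is kept, amend 9.1.1 and 7.10 to match. Relabel the SAP 8 tables as treatment-related adverse events plus all SAEs and events of clinical interest, and say that the last group is included, since the SAP's note mentions SAEs only. Relabelling keeps the unrelated SAE data, which deleting the tables would lose. This costs text edits only.
3. In protocol 2.2.1.1 and 13.1.1 and SAP 9.1.1, state whether 'treatment-related' qualifies discontinuation.
4. In SAP 9.2.2, derive discontinuations from the withdrawal CRF as well as the AE and SAE forms.
5. Report the co-primary under the other reading as a sensitivity analysis. This is one further run of a model already programmed.

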### **9.2 Reporting Procedure**

#### **9.2.1 Site**

##### **9.2.1.1 Adverse Events**

AEs should be reported on an AE Form (and where applicable on an SAE Form). An AE Form should be completed at each visit and returned to the PePS2 Trial Office.

AEs will be reviewed using the Common Terminology Criteria for Adverse Events (CTCAE), version 4.0 (see Appendix 6). Any AEs experienced by the patient but not included in the CTCAE should be graded by an Investigator and recorded on the AE Form using a scale of (1) mild, (2) moderate or (3) severe. For each sign/symptom, any changes in grade should be documented.

##### **9.2.1.2 Serious Adverse Events**

For more detailed instructions on Serious Adverse Event (SAE) reporting refer to the SAE Form Completion Guidelines contained in section 5 of the ISF.

AEs defined as serious and which require reporting as an SAE should be reported on an SAE Form. When completing the form, the Investigator will be asked to define the causality and the severity of the AE which should be documented using the CTCAE version 4.0.

On becoming aware that a patient has experienced an SAE, the Investigator (or delegate) must complete, date and sign an SAE Form. The form should be faxed together with a SAE Fax Cover Sheet to the PePS2 Trial Office using one of the numbers listed below as soon as possible and no later than 24 hours after first becoming aware of the event:

To report an SAE, fax the SAE Form with an SAE Fax Cover Sheet to:

**[name] (primary) or [name] (secondary)**

On receipt the PePS2 Trial Office will allocate each SAE a unique reference number. This number will be transcribed onto the SAE Fax Cover Sheet which will then be faxed back to the site as proof of receipt. If confirmation of receipt is not received within 1 working day please contact the PePS2 Trial Office. The SAE reference number should be quoted on all correspondence and follow-up reports regarding the SAE. The SAE Fax Cover Sheet completed by the PePS2 Trial Office should be filed with the SAE Form in the ISF.

For SAE Forms completed by someone other than the Investigator, the Investigator will be required to countersign the original SAE Form to confirm agreement with the causality and severity assessments. The form should then be returned to the PePS2 Trial Office in the post and a copy kept in the ISF. Investigators should also report SAEs to their own Trust in accordance with local practice.

#### **9.2.1.3 *Events of Clinical Interest***

ECI must be reported within 24 hours to the PePS2 Trial Office. For the time period beginning when the consent form is signed until treatment allocation, any ECI, or follow up to an ECI, that occurs to any subject must be reported within 24 hours to the PePS2 Trial Office if it causes the subject to be excluded from the trial, or is the result of a protocol-specified intervention, including but not limited to washout or discontinuation of usual therapy, diet or a procedure.

For the time period beginning at treatment allocation through 6 months following cessation of treatment, or 30 days following cessation of treatment if the subject initiates new anticancer therapy, whichever is earlier, any ECI, or follow up to an ECI, whether or not related to pembrolizumab, must be reported within 24 hours to the Trial Office.

#### **9.2.1.4 *Provision of Follow-up Information***

Patients should be followed up until resolution or stabilisation of the Follow-up information should be provided on a new SAE Form (refer to the SAE Form Completion Guidelines for further information).

### **9.2.2 PePS2 Trial Office**

On receipt of an SAE Form, seriousness and causality will be determined independently by a Clinical Coordinator. An SAE judged by the Investigator or Clinical Coordinator to have a reasonable causal relationship with the trial medication will be regarded as a Serious Adverse Reaction (SAR). The Clinical Coordinator will also assess all SARs for expectedness. If the event meets the definition of a SAR that is unexpected (i.e. is not defined in the Reference Safety Information) it will be classified as a Suspected Unexpected Serious Adverse Reaction (SUSAR).

### **9.2.3 Reporting to the Competent Authority and Research Ethics Committee**

#### **9.2.3.1 Suspected Unexpected Serious Adverse Reactions**

The PePS2 Trial Office will report a minimal data set of all individual events categorised as a fatal or life threatening SUSAR to the Medicines and Healthcare products Regulatory Agency (MHRA) and Research Ethics Committee (REC) within 7 days. Detailed follow-up information will be provided within an additional 8 days.

All other events categorised as SUSARs will be reported within 15 days.

#### **9.2.3.2 Serious Adverse Reactions**

The PePS2 Trial Office will report details of all SARs (including SUSARs) to the MHRA and main REC annually from the date of the Clinical Trial Authorisation, in the form of a Developmental Safety Update Report.

#### **9.2.3.3 Adverse Events**

Details of all AEs will be reported to the MHRA on request.

#### **9.2.3.4 Other safety issues identified during the course of the trial**

The MHRA and REC will be notified immediately if a significant safety issue is identified during the course of the trial.

### **9.2.4 Investigators**

Details of all SUSARs and any other safety issue which arises during the course of the trial will be reported to Principal Investigators. A copy of any such correspondence should be filed in the ISF.

### **9.2.5 Trial Steering Committee**

The Trial Steering Committee will review all SAEs.

### **9.2.6 Manufacturer of Investigational Medicinal Product**

All SAEs will be reported to Merck, Sharp and Dohme, the manufacturer of the Investigational Medicinal Product, within an agreed timeframe from first awareness of the event of the PePS2 Trial Office during the reporting period.

## **10 DATA HANDLING AND RECORD KEEPING**

### **10.1 Data Collection**

#### **10.1.1 Case Report Form (CRF)**

The CRF will comprise a set of forms capturing details of eligibility, baseline characteristics, treatment and outcome details. This trial will use an electronic remote data capture (eRDC)

system which will be used for completion of CRF. Access to the eRDC system will be granted to individuals via the Trial Office. Pre-screening Registration, SAE reporting and Notification of Pregnancy will be paper-based.

The CRF must be completed by the Investigator or an authorised member of the site research team (as delegated on the Site Signature and Delegation Log) within specified timeframes (found in the CRF completion guidelines). The exceptions to this are the SAE Form, which must be co-signed by the Investigator and reported in an expedited manner.

Data reported on each form should be consistent with the source data or the discrepancies should be explained. If information is not known, this must be clearly indicated on the form. All missing and ambiguous data will be queried. All sections are to be completed. CRF guidelines will be provided. In all cases it remains the responsibility of the Investigator to ensure that the CRF has been completed correctly and that the data are accurate.

The format and questions in the CRF may be amended by the Trial Office, as appropriate, throughout the duration of the trial. Whilst this will not constitute a protocol amendment, sites will be notified of new versions of the form when they are available in the eRDC system, and in the case of the SAE form, new versions of the form must be implemented by participating sites immediately on receipt.

## 10.2 Archiving

It is the responsibility of the Principal Investigator to ensure all essential trial documentation and source records (e.g. signed Informed Consent Forms, Investigator Site Files, Pharmacy Files, patients' hospital notes, copies of CRFs etc.) at their site are securely retained for at least 25 years after the end of the trial or following the processing of all biological material collected for research, whichever is the later. Do not destroy any documents without prior approval from the PePS2 Trial Office.

# 11 QUALITY MANAGEMENT

## 11.1 Site Set-up and Initiation

All sites will be required to sign a Clinical Trial Site Agreement prior to participation. In addition all participating Investigators will be asked to sign the necessary agreements and registration forms; and supply a current CV to the PePS2 Trial Office. All members of the site research team will also be required to sign the Site Signature and Delegation Log, which should be returned to the PePS2 Trial Office. Prior to commencing recruitment all sites will undergo a process of initiation. Key members of the site research team will be required to attend either a meeting or a teleconference covering aspects of the trial design, protocol procedures, AE reporting, collection and reporting of data and record keeping. Sites will be provided with an Investigator Site File and a Pharmacy File containing essential documentation, instructions, and other documentation required for the conduct of the trial.

The PePS2 Trial Office must be informed immediately of any change in the site research team.

